## 12. DATA BASE MANAGEMENT AND REPORTS

This task includes the treatment of the variables obtained during the data collection period. In order to assure the confidentiality of the participants an ID code will be attributed to each participant in the database and all the equipment's and sheets used. A single researcher will perform the database management.

### EXPECTED RESULTS

We expect to add the data collected at M0, M1, M2 and M3 to the database within 2 weeks of the end of the respective evaluation moment, and store it at the FMH-UL web server allowing detailed progress reports and back-ups when needed. Individual reports will be delivered within 2 weeks of the end of the respective evaluation moment.

---

### 13. STATISTICAL ANALYSIS

Data will be analyzed in M0, M1, M2 and M3. It will be tested the data for normality and homogeneity of variance with the Shapiro Wilk and Levene's tests, respectively. Data analysis will be described according to the established purposes for this project (descriptive values: mean, standard deviation, range, % change) and comparisons of means will be used for all purposed outcomes intra and inter groups. Baseline characteristics between groups will be evaluated with oneway ANOVA. Mixed between within subjects ANOVA will be conducted in a 2 (pre vs post ET) design to assess efficiency of the program. When a significant interaction is observed, t tests, or Wilcoxon signed-rank tests will be used to determine where the interaction occurred.

M0 versus M1, M0 versus M2, M0 versus M3, M1 versus M2, M2 versus M3 and M1 versus M3 will be compared to evaluate the changes in patients and trace the necessary timespan for such changes using General Linear Mixed Model Analysis for repeated measures with Tukey's posthoc procedure for the mean comparisons. Pearson product moment correlation coefficient or Spearman's rank correlation coefficient will be used to study the relationship between different variables by group and correlation coefficients will be compared between groups. Statistical significance will be set at an alpha level of 0.05. Other statistical procedures can be done.

Statistical analyses will be conducted using Statistical Package for the Social Sciences (SPSS) 22.0 (IBM SPSS Statistics, Chicago, IL, USA).

Data analysis will allow peer reviews redaction, slide presentations and oral communications in national and international conferences at the end of 2017 beginning of 2018.

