## METHODS

### PARTICIPANTS

Patients with CVD that underwent to a hospital-based CR program in the Lisbon district Hospitals will be recruited. The study will be performed in the Cardiovascular Rehabilitation Center of the University of Lisbon (CRECUL) at the Lisbon University Stadium (EUL). The participants will be randomized into one of the following exercise groups: 1) periodized group; 2) non periodized group following the American College of Sports and Medicine (ACSM) guidelines. Patient's eligibility will be assessed according to the risk stratification criteria for patients with CVD for low and/or moderate risk stratification from the American Association of Cardiovascular and Pulmonary Rehabilitation. Male and female participants, ≥ 18 years of age, who had an established history of the following conditions or procedures will be included: MI, or coronary revascularization (coronary artery bypass grafting, percutaneous transluminal coronary angioplasty, or coronary artery stent), angina pectoris or coronary artery disease defined by angiography. Exclusion criteria

will be participants who had heart failure, heart transplants with either cardiac resynchronization therapy or implantable defibrillators; inability to comply with guidelines for participation in exercise testing and training; and significant limiting and/or unstable comorbidities that would prevent full participation.

Sample size was calculated (G-Power, *Version 3.1.3*) assuming a difference in peak oxygen uptake (VO2 peak) between groups of 3 ml/kg/min to be a clinically important difference with a SD of 3.5 ml/kg/min,  $\alpha=0.05$ ,  $1-\beta=0.80$  and an expected dropout rate of 37%. The calculations yielded a total minimum sample size of 50 participants (25 in each group).

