## STUDY DESIGN

A longitudinal RCT research design using two distinct ET prescriptions (periodization vs non periodization) will be applied in CVD patients. Briefly, following the informed consent process, patients will be randomized and stratified (by gender and age) to periodization or non periodization groups. The randomization code will be developed with a computer random-number generator to select random permuted blocks. Participants will exercise for a period of 12 months. All the same assessments, except the echocardiogram that will be done in M0 and M3 (for risk stratification), are going to be taken in 4 different time points during a year: M0 - baseline, M1 - 3 months after starting the ET, M2 - 6 months after starting the ET and M3 - 12 months after starting the ET. The patients will be randomized into either one of the two ET groups. Recruitment and screening will last 12 months (September 2017 to September 2018) and the patient assessment will last until September 2019. It is expected to finish the project with peer-review redaction submitted and/or accepted in December 2019.

The following assessments on the 4 time points will be performed at the Pulido Valente Hospital, FMH-UL and Academia de Fitness at EUL: Echocardiogram (Echo) (MyLab Alpha, ESAOTE); cardiopulmonary exercise test (CPET) (Ergostik, Geratherm Respiratory GmbH, Bad Kissingen); skeletal muscle deoxygenation dynamics (NIMO, Nirox srl); body composition - dual energy radiographic absorptiometry (DXA, Hologic Explorer-W); objective measured physical activity - accelerometer (ActiGraph GT3X+); functional physical fitness - Fullerton Functional Fitness Test; isometric strength – portable hand dynamometer JAMAR plus digital (Sammons Preston); maximal strength – 1RM and Quality of Life questionnaire.

All assessment moments will be done in 1 to 2 weeks:

Day 1 – Echo and CPET will be performed at the Pulido Valente Hospital;

Day 2 and 3 – during the day and time of the ET session at the EUL, the patient will perform: functional physical fitness tests; maximal strength; isometric strength and Quality of Life questionnaire;

Day 4 – In FMH, the dual energy radiographic absorptiometry (DXA) exam and the activation of the accelerometer to measure the objective measured physical activity will be done.

Day 5 – Submaximal CPET with the skeletal muscle deoxygenation dynamics at the Pulido Valente Hospital.

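### The programme-efficiency test is a two-level pre/post ANOVA that leaves out the baseline covariate, gender, age and the interim visits; a baseline-adjusted model is a modest, low-cost improvement

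*Combined protocol and SAP*

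**What the plan says.** Section 13 (Statistical Analysis) links one test to whether the programme works: "Mixed between within subjects ANOVA will be conducted in a 2 (pre vs post ET) design to assess efficiency of the program". The sentence does not write out the group factor. It follows from the term between-within and from the next sentence: "When a significant interaction is observed, t tests, or Wilcoxon signed-rank tests will be used to determine where the interaction occurred". No covariate is named. The post-training visit is not identified; the 12-month assessment (M3) is the natural reading of Study Design.

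The same section states "Data will be analyzed in M0, M1, M2 and M3" and "comparisons of means will be used for all purposed outcomes intra and inter groups", without naming a model for either. A four-visit model appears next, for the six pairwise visit comparisons, with a stated purpose: "to evaluate the changes in patients and trace the necessary timespan for such changes using General Linear Mixed Model Analysis for repeated measures". It is given no group term, group-by-visit term or covariate.

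Study Design says that "patients will be randomized and stratified (by gender and age) to periodization or non periodization groups". Section 13 uses neither factor in any analysis. The sample size, under Participants, assumes a difference in VO2 peak "between groups of 3 ml/kg/min to be a clinically important difference with a SD of 3.5 ml/kg/min" and "an expected dropout rate of 37" per cent, and arrives at 25 per group.

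**The concern.** The trial exists to compare two training regimes, and the one test aimed at that comparison leaves out information that the trial collects anyway. Entering M0 only as the pre level forces its coefficient to 1, as in any change score; a covariate lets the data set the coefficient. Analysing without the stratification factors departs from the design. If more than a third of participants leave, a change score needing both M0 and M3 also drops those with values at 3 months (M1) or 6 months (M2) but not at M3. The stake is the width of the interval for the 12-month difference, and so the power, in a trial of 50.

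**Working it through.** **Inputs from the plan.** Difference 3 ml/kg/min, SD 3.5, alpha 0.05, power 0.80, dropout 37%, 25 per group.

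**Assumed, because the documents do not say.** r from 0.5 to 0.9, equal at all visits; random dropout; two-sided testing; SD 3.5 as the SD of change, with the single-visit reading as an alternative.

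**The plan's own figure.** A one-sided t test needs 18 per arm, and 18 x 1.37 = 24.7, so 25 per arm and 50 in total. A two-sided t test needs 23 per arm before dropout, and no two-sided variant tried gives 50. This is a separate matter; it matters here because sidedness is unstated.

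**Completers.** 50 x 0.63 = 31.5, taken as 16 per arm, if every dropout lacks M3.

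**The test as written.** Standard error = 3.5 x sqrt(2/16) = 1.237. Noncentrality = 3/1.237 = 2.42 on 30 df. Two-sided power is 65.0%. The 95% CI half-width is about 2.042 x 1.237 = 2.5 ml/kg/min.

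**Baseline adjustment.** With single-visit SD s, the variance of change is 2(1-r)s^2, and the variance after adjusting for baseline is (1-r^2)s^2. The ratio is (1+r)/2, a cut of (1-r)/2.

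| r | Variance cut | Power, formula (29 df) | Power, simulated | CI half-width, formula |
|---|---|---|---|---|
| 0.5 | 25% | 77.2% | 76% | 2.19 |
| 0.7 | 15% | 72.0% | 71% | 2.33 |
| 0.8 | 10% | 69.5% | 68 to 69% | 2.40 |
| 0.9 | 5% | 67.2% | 65% | 2.47 |

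The half-width is 2.045 x 1.237 x sqrt((1+r)/2). The formulas ignore chance baseline imbalance, so the simulated power is the better guide; its Monte Carlo error is up to about a point.

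**Other readings, by formula.** If 3.5 is the single-visit SD, the SD of change is 3.50, 2.71, 2.21 and 1.57, and power goes from 65.0%, 85.7%, 96.0% and over 99% to 77.2%, 90.7%, 97.4% and over 99%. One-sided, with 3.5 as the SD of change, it goes from 76.6% to 86.2%, 82.2%, 80.2% and 78.3%.

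**Repeated-measures mixed model.** Simulated with 25 per arm, 9 random dropouts per arm, unstructured covariance, Satterthwaite degrees of freedom, and gender and age given no effect (the unfavourable case). Against 65% for pre/post, power was 74-78%, 68-75%, 66-72% and 63-70% at the four values of r. The low end has all dropout before M1, the high end all after M2. Type I error was 0.041 to 0.053.

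**Cost of gender and age.** If they are balanced and unrelated to outcome, going from 29 to 27 df costs about 0.2 points. Where the simulation left them unbalanced, the cost was about 2 points. No gain can be computed, because the documents give no association with outcome.

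**The case against.** The pre/post test is legitimate. It already compares change from M0, so baseline is not ignored, and section 13 promises between-group comparisons and names a mixed model that could hold a group term. M1 and M2 do enter the six visit comparisons. The gain rests on an unknown r and is slight when r is high; at r = 0.9 with all dropout before M1, the mixed model loses about 2 points. That model carries 11 mean parameters, estimated from perhaps 32 people.

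Most of this stands, and it limits the point to efficiency. It does not supply the adjustment. The line on between-group means names no model. The remark in the body-composition section that DXA data will allow adjustments names neither a model nor outcome baseline, gender or age. The allowance for other procedures in section 13 commits to nothing.

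A reader might infer that the result will be biased by analysing completers only. The documents do not support that. It would need dropout to relate to outcome differently by arm. They give no sign of this, and the Background reports that neither interval nor resistance training has been shown to harm adherence. A reader might also infer that no between-group analysis is planned, or that the undefined post visit is an error. The first is contradicted by the interaction test; the second is missing detail.

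**Conclusion.** The point holds as a low-cost improvement, not as an error that biases the result. The efficiency test is valid under randomization if dropout is not selective, but it gives up some precision. On the two-sided, SD-of-change reading with 16 completers per arm, baseline adjustment alone is worth about 11 points of power at r = 0.5, 6 at 0.7, 3 to 4 at 0.8 and nothing at 0.9. The mixed model changes power by between -2 and +12 points, depending on r and on when people leave. If 3.5 is the single-visit SD, power is already 96% or more at r of 0.8 and above, so little can be gained. All figures are for VO2 peak only. The case for gender and age is consistency with the stratified design, not a demonstrated gain.

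**What to change.** State that the between-group result is the M3 difference with its 95% CI, by assigned group, from a baseline-adjusted model, and state the sidedness of the test.

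- **Preferred:** the repeated-measures mixed model already named, with M1, M2 and M3 as outcomes; group, visit and group-by-visit; baseline with its visit interaction; gender and age. Name a small-sample degrees-of-freedom method, such as Satterthwaite, and a simpler covariance structure in case the unstructured one does not converge. Note that participants with no visit after M0 contribute no outcome.
- **Minimum:** ANCOVA of M3 on group and baseline.
- **Keep** the pre/post ANOVA as a sensitivity analysis, with the post visit defined.

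The cost is a few sentences in the analysis section and a little more analysis work, with no new data. The drawbacks are the power costs of gender and age shown above (about 0.2 points if balanced, about 2 if not, when they are unrelated to outcome) and, for the mixed model, reliance on dropout being explained by observed values.

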Periodization was developed in the 1960's by the Russian physiologist Leo Matveyev and is defined as an organized cyclic program that uses planned variations in intensity, volume, and specificity to minimize fatigue and maximize performance outcomes. Periodized programs are composed of macrocycles, mesocycles and microcycles. The largest cycle or macrocycle is 1 year in length, each macrocycle is then broken into mesocycles, traditionally 1 to 3 months in length. Finally, each mesocycle is broken into individual microcycles. In healthy or trained populations, periodization aims to optimize ET adaptations as compared with non periodized training, to prevent overtraining and to avoid plateauing of training adaptations. The classical approach to periodization is linear periodized training, consisting in promoting wave-like progression, typically moving from general training (high volume/low intensity) towards specific training (low volume/high intensity). Periodized methods are considered to be superior to nonperiodized methods in trained populations and appears to be superior in inactive adults. Interestingly, a recent study investigated the effect of 22 weeks of 2 different types of periodization and 1 non periodization RT protocols on a comprehensive range of physical function and health outcomes in apparently healthy untrained older adults. Contrary of what was hypothesised, all three training models were equally effective for promoting significant improvements in various physical function and physiological health outcomes through RT in this population.

In most of the CR programs there are no periodization or exercise progression during medium to long term interventions. Further randomized controlled trials (RCT) are necessary to evaluate long-term periodization outcomes and assess the length of change observed in supervised CR programs.

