## PURPOSE

To overcome the lack of knowledge regarding the physiological effects after hospital-based CR program, a 12 month RCT study will be performed. This study will hopefully contribute to generate evidence-based exercise prescription approaches to prolong the ET after the end of hospital-based CR programs.

The purpose of this research project is twofold:

1) To conduct a 12-month randomized control trial to evaluate the effects of periodized ET regime versus a non periodized ET regime on VO2 peak, maximal strength, body composition, functionality and quality of life in CVD patients.

2) to differentiate the effects of a 12-month periodized ET regime versus a non periodized ET regime on the different components of the oxygen kinetics response and oxidative adaptations in CVD patients.

The primary end points for aim 1 are: cardiopulmonary exercise testing (CPET) variables such as VO2 peak, AT, peak work rate, ventilatory equivalent of carbon dioxide (VE/VCO2), ventilatory equivalent of oxygen (VE/VO2), minute ventilation (VE), one repetition maximum (1RM), total body bone mineral content, lean and fat tissue mass and percentage of body fat mass, quality of life and functional physical fitness tests. The primary end points for aim 2 are oxygen kinetics and muscle deoxygenation dynamics of the vastus lateralis muscle at the submaximal test.

The hypothesis for this study are: 1) considering that this type of periodization exerts higher stress on the cardiovascular and neuromuscular systems, so that there could be greater adaptations, leading to higher increases in VO2max, muscle strength, body composition and functionality compared to non periodized ET regime; 2) there will be a better improvement microvascular O2 delivery in the exercise transient in response to periodized ET regime that would be associated with a faster adjustment of pulmonary VO2 kinetics than in non periodized group. Improvements in microvascular O2 delivery would be indicated by a better matching between the rate of adjustment of muscle deoxygenation relative to phase II pulmonary VO2, which represents a decreased reliance on O2 extraction for a given pulmonary VO2.

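### No between-arm difference in change with a confidence interval is specified at M1, M2 or M3, and the follow-up tests that are named do not supply one

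*Combined protocol and SAP*

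**What the plan says.** The question is a comparison of arms. Purpose: "To conduct a 12-month randomized control trial to evaluate the effects of periodized ET regime versus a non periodized ET regime". Background gives timing as part of the reason for such trials: "Further randomized controlled trials (RCT) are necessary to evaluate long-term periodization outcomes and assess the length of change observed in supervised CR programs". Study Design schedules the outcome assessments at baseline (M0) and at 3, 6 and 12 months (M1, M2, M3). Only the echocardiogram is limited to M0 and M3.

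Section 13 then sets out:

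- The main model: "Mixed between within subjects ANOVA will be conducted in a 2 (pre vs post ET) design to assess efficiency of the program". It does not say which visit is the post visit.
- The follow-up: "When a significant interaction is observed, t tests, or Wilcoxon signed-rank tests will be used to determine where the interaction occurred".
- All six pairs of visits, which "will be compared to evaluate the changes in patients and trace the necessary timespan for such changes", by "General Linear Mixed Model Analysis for repeated measures with Tukey's posthoc procedure for the mean comparisons". Neither group nor a group x visit term is mentioned.
- A general statement that means will be compared within and between groups for every outcome, and that data will be analysed at all four visits. No visit, contrast, test or interval is attached to it.

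Participants bases the sample size on a difference "between groups of 3 ml/kg/min to be a clinically important difference with a SD of 3.5 ml/kg/min", with 37% dropout and 25 patients per arm.

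**The concern.** The trial measures both arms at three follow-up visits and asks whether one regimen does better. Its results should therefore include, for each visit, the difference between arms in change from baseline, with an interval. The tools that section 13 names in detail do not produce this. One is paired, one is of unstated type, and the third compares visits with visits.

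The documents expect both arms to improve (expected results for the cardiopulmonary exercise test and for the functional fitness tests). In that setting, within-arm tests say least about the difference between regimens, because significant change in both arms is compatible with a large difference or with none. At stake is a report that can say the arms differ pre v post, but has no planned estimate of when the difference appears or how large it is.

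**Working it through.** **1. The plan's own figure.** The plan gives no figure for this point. Its only computed statistical figure is the total of 50. A one-sided two-sample t test (difference 3, SD 3.5, alpha 0.05, power 0.80) needs 18 per arm; 18 × 1.37 = 24.7, rounded up to 25 per arm, or 50. A two-sided test needs 23 per arm, and 23 × 1.37 = 31.5, so 32. The plan does not state sidedness. That is a separate matter; the calculation matters here only because its target is a between-arm difference.

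**2. What the pre v post interaction tests.** The interaction contrast in a 2 (group) × 2 (time) design is

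(post − pre, periodized) − (post − pre, non periodized),

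which is the between-arm difference in mean change. Its F statistic equals the square of the two-sample t statistic on change scores. On one simulated data set both came to 0.04471. So the plan does contain a valid between-arm test, for one interval.

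**3. What the other named tools compare.**

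| Tool in section 13 | Compares | Between-arm difference at a visit? |
|---|---|---|
| Wilcoxon signed-rank | two times within the same patients | No |
| t tests | not stated (paired or independent) | Only if independent; not specified |
| Tukey contrasts in the mixed model | visit with visit; group not mentioned | No |
| General promise of between-group comparisons | not stated | Not specified |

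**4. Why within-arm tests cannot stand in.** Take 16 completers per arm, from 25 × (1 − 0.37) = 15.75, and suppose that the SD of change is 3.5 in each arm.

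- Within-arm change needed for significance (paired t): 2.131 × 3.5/√16 = 1.86 ml/kg/min.
- 95% half-width for the between-arm difference: 2.042 × 3.5 × √(2/16) = 2.53.

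Three illustrative sets of observed changes (not error rates):

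| Changes in the two arms | Within-arm result | Between-arm difference (95% CI) |
|---|---|---|
| 5 and 2 | both significant | 3 (0.47 to 5.53) |
| 4.5 and 1.5 | one significant, one not | 3 (0.47 to 5.53) |
| 2 and 1.5 | one significant, one not | 0.5 (−2.03 to 3.03) |

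Rows 1 and 2 have the same between-arm result but different within-arm patterns. Rows 2 and 3 have the same pattern but different between-arm results. A Tukey adjustment moves the 1.86 threshold but not this logic.

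**5. Precision of the missing estimates.** Half-width = t × SD of change × √(2/n).

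- n = 16: 2.53, as above.
- n = 25: 2.011 × 3.5 × √(2/25) = 1.99.

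With dropout spread over the year, M1 and M2 would lie between these. Participants does not say whether 3.5 is an SD of level or of change. If it is an SD of level, the SD of change is 3.5 × √(2(1 − r)). At r = 0.5 this is 3.5 and nothing alters. At r = 0.6 the half-widths are multiplied by 0.894 (2.26 and 1.78), and at r = 0.9 by 0.447 (1.13 and 0.89). The values of r are assumptions.

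**6. Power and multiplicity.** With SD of change 3.5, two-sided power for a difference of 3 at M3 is 65% with 16 per arm and 84% with 25. If all three visits were tested at 0.05 with no gate and no true difference, simulation (correlation between changes 0.3 to 0.7) gives a familywise error of 11 to 14% per outcome. That is a reason to name one main contrast.

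**The case against.** The strongest reply is that section 13 does compare the arms. The interaction is a between-arm test of change, and the section promises comparisons between groups for all outcomes at four visits. This stands in part. A reader who inferred that the plan makes no between-arm comparison would be wrong. But the promise names no contrast, test, visit or interval, and the interaction covers one interval with an undefined end.

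Second, after a two-level ANOVA, finding where the interaction occurred most naturally means finding which simple effect is responsible, not which visit. This also stands. The sentence cannot be faulted for failing at a task it may not have been given. The absence of by-visit estimates remains.

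Three stronger readings are tempting and are not supported:

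- **Inflated false positives.** Follow-up takes place only after a significant interaction, and that test holds its level. If both arms truly change equally by 1.0 to 2.0 ml/kg/min (15 or 25 per arm, assumed pre-post correlation 0.7 to 0.8), a false interaction together with discordant within-arm paired t tests occurs in 0.6 to 4.6% of simulated trials.
- **A known rate of pointing to the wrong visit.** Any such percentage would require linking the interaction test to the Tukey comparisons, which section 13 does not do. It would also require a rule that a visit differs when exactly one arm changes significantly, which the plan does not state.
- **Arms that separate only after M1, because Table 2 gives them equal load in sessions 1 to 15.** Table 2 matches daily TRIMP in every row by design. Work zones differ from session 16 (4 v 3), and at three sessions a week M1 falls near sessions 36 to 39.

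**Conclusion.** The point holds as a gap in specification. Beyond one pre v post interaction test and a general promise, section 13 specifies no between-arm difference in change, and no interval for it, at M1, M2 or M3. The paired, untyped and visit-versus-visit tools it names cannot show when, or by how much, the regimens differ.

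This is a minor point and a cheap improvement. It implies no bias and no inflated error in the interaction test. The conclusion rests on the wording alone. The precision figures rest on an assumed SD of change of 3.5 ml/kg/min and on 16 to 25 patients per arm.

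**What to change.** Replace the follow-up sentence in section 13 with a paragraph to this effect:

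- The planned mixed model includes group, visit and group x visit.
- The main between-arm contrast is the difference in change from M0 to M3, which also settles which visit is the post visit.
- The between-arm difference in change from M0 is reported at M1, M2 and M3, each with a 95% confidence interval. M1 and M2 are supportive estimates.
- Within-arm paired t and signed-rank tests are descriptive and are not used as evidence that the regimens differ.
- Where a rank test of the arms is needed, it is a two-sample test (Mann-Whitney) on change.

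The cost is one paragraph and three contrasts per outcome, with the same data and software. Power at M3 is unchanged, because that contrast keeps the full 0.05.

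Formal testing across visits is optional. A fixed order M3, M2, M1 protects the error rate but dates onset poorly. With assumed gaps of 1, 2 and 3 ml/kg/min at M1, M2 and M3 (SD 3.5, correlation 0.3 to 0.7, 16 or 25 per arm), and given a significant M3, it declares M2 in about 41 to 60% of trials and M1 in about 9 to 18%. Holm across the three visits lowers M3 power from 65% to about 47% (16 per arm) and from 84% to about 71% (25 per arm) if only M3 differs. The estimates with intervals are the part worth having.

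### The time needed for change has no defined reading rule; if it is read from which visit pairs are significant, it depends on sample size and unequal visit gaps as well as on when patients improve.

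*Combined protocol and SAP*

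**What the plan says.** Section 13 of the combined protocol and SAP names the comparisons: "M0 versus M1, M0 versus M2, M0 versus M3, M1 versus M2, M2 versus M3 and M1 versus M3 will be compared". The same sentence gives their purpose and the model, in that the pairs "will be compared to evaluate the changes in patients and trace the necessary timespan for such changes using General Linear Mixed Model Analysis", and the decision tool, "with Tukey's posthoc procedure for the mean comparisons". The threshold follows shortly after: "Statistical significance will be set at an alpha level of 0.05". Study Design fixes the follow-up visits: "M1 - 3 months after starting the ET, M2 - 6 months after starting the ET and M3 - 12 months after" the start of training. The gaps are therefore 3, 3 and 6 months.

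Section 13 also lists descriptive output (mean, SD, range, % change) but does not tie it to the timespan. It plans no confidence intervals, no rate per month and no size of change that would count. The only clinically important difference in the document is in the sample size paragraph of Participants, "between groups of 3 ml/kg/min to be a clinically important difference with a SD of 3.5 ml/kg/min". That is a between-group quantity and is not used to define change over time within patients.

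**The concern.** A Tukey comparison of two visit means returns an estimate and a significance verdict. With no other criterion stated, the verdict is the only operative tool for saying how long change takes. A significant difference needs the observed change to exceed a critical value that shrinks as the number of patients grows. So the first visit to differ from M0 tends to come earlier in a larger sample, even when patients improve at the same pace. The same critical value applies to a 3-month gap and to a 6-month gap, so a steady monthly gain is more likely to be declared over M2 to M3 than over M0 to M1 or M1 to M2.

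Two mistaken conclusions become likely. One is a plateau between 3 and 6 months when gain was steady. The other is a different timespan for each regime when the two trajectories are the same. The Background gives the duration of change in supervised programmes as one reason for the trial, so such statements may well reach the report.

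**Working it through.** The plan states no figure for the timespan analysis, so there is none to reproduce. The check asks what six Tukey comparisons would return under a known, steady course.

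**Inputs**
- Visits at 0, 3, 6 and 12 months (Study Design); alpha 0.05 and Tukey for four means (Section 13).
- 25 patients per arm (Participants). With the stated 37% dropout, 25 × 0.63 = 15.75, so about 16 completers.
- 12-month gain: the expected results for the cardiopulmonary test give 5 to 15%. Baseline is not given. An assumed baseline of 20 ml/kg/min makes this 1 to 3, with central value 2.
- SD of change (assumed): 2.77, from the SDs of 3.1 and 2.4 that the Background quotes for two training types: √((3.1² + 2.4²)/2) = 2.77.
- Also assumed: compound symmetry, complete data, and each arm analysed separately. Section 13 does not say whether these comparisons are by arm or pooled.

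**Smallest significant difference, n = 25.** The error df is 3 × 24 = 72 and the Tukey multiplier (q/√2) is 2.630. The standard error of any visit difference is 2.77/√25 = 0.554. The critical difference is 2.630 × 0.554 = 1.46 ml/kg/min, whichever pair is tested.

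**Effect of gap length.** A steady gain of 2 over 12 months is 0.167 per month, so the true means are 0, 0.5, 1.0 and 2.0.
- M1 to M2 (true change 0.5): (0.5 − 1.46)/0.554 = −1.73, a probability of about 4%.
- M2 to M3 (true change 1.0): (1.0 − 1.46)/0.554 = −0.83, about 20%.

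Simulation gives 4 to 5% and 21%. The monthly rate is the same in both intervals.

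**First visit significantly different from M0, same true course (simulated)**

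| n per analysis | M1 | M2 | M3 | none |
|---|---|---|---|---|
| 16 | 3% | 10% | 47% | 40% |
| 25 | 5% | 18% | 61% | 16% |
| 32 | 6% | 24% | 63% | 7% |
| 64 | 13% | 51% | 36% | 0% |

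**Two arms, identical courses, 25 each.** The probability of different answers is 1 − (0.05² + 0.18² + 0.61² + 0.16²) = 1 − 0.433 = 0.57. With a gain of 1 it is 38%, because most arms then show no significant visit (77%). With a gain of 3 it is 59%.

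**Does the true course matter?** Yes. With n = 25 and a gain of 2, an early-rising course (assumed time constant 3 months) is first significant at 3 months in 38% of runs, against 5% for the steady course.

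**Other inputs.** With a visit SD of 3.5 (the sample size SD), an assumed within-patient correlation of 0.8 and n = 25, the steady course gives M1 to M2 7% and M2 to M3 36%. Across correlations of 0.7 to 0.9 the pairs run from 5% against 22% to 16% against 71%. The direction does not change.

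**What estimation would give, n = 25.** With t = 1.99, the 95% half-width for a visit difference is 1.99 × 0.554 = 1.10. Per month this is 1.10/3 = 0.37 for a 3-month interval and 1.10/6 = 0.18 for the 6-month interval, against a true 0.167 in each. Gap length then changes the precision and leaves the expected answer alone.

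**The case against.** The strongest reply is that Section 13 never says the timespan is the first significant visit, never says that a non-significant M1 to M2 means a plateau, and does plan means and % change. Each pair is a legitimate contrast between dated visits, and Tukey handles multiplicity across the six. This stands in part: the significance rule is an inference from the only tool named, so the point has to be conditional. It does not remove the gap, because the descriptive output is not linked to the timespan and no other criterion is given.

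Three stronger readings are tempting, and the documents do not support them.
- A reader might infer that the result would be an artefact, unrelated to when patients improve. The 38% against 5% contrast shows that the method does respond to the true course.
- A reader might infer that this trial's most likely answer would move from 12 to 6 months through sample size alone. In the main illustration that takes about 64 patients per analysis; with 16 to 25 per arm, 12 months remains the most likely answer, although the probabilities shift.
- A reader might infer that the trial's main conclusions are at risk. The aims and hypotheses in the Purpose section compare regimes and do not concern time course.

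It is also fair to say that piecewise slopes with knots at 3 and 6 months are saturated with these four visits. Each slope is an adjacent-visit difference divided by months, with the same test statistic, so re-expression adds no power.

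**Conclusion.** The concern holds in conditional form. The plan leaves the timespan undefined and offers only Tukey-adjusted significance to find it. Read that way, the answer mixes the true course with sample size and gap length. At the planned 25 per arm, a steady gain of 2 is about four to five times as likely to be significant over M2 to M3 as over M1 to M2, and identical arms disagree in about 57% of trials (38 to 59% for gains of 1 to 3). These percentages rest on the assumed baseline, SD of change, compound symmetry, steady course and separate analysis by arm, and are illustrative. The gap effect has the same direction under every alternative tried. The matter is secondary: it is worth correcting before analysis, and it does not alter the comparison of the two regimes.

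**What to change.** In Section 13, state that neither the timespan nor a plateau will be inferred from which visit pairs are significant. From the same mixed model, with arm, visit and their interaction, report:
1. mean change from M0 with 95% CI at each visit, by arm;
2. change per month with 95% CI over 0–3, 3–6 and 6–12 months, by arm;
3. the between-arm difference in each of these, with 95% CI, as the basis for any statement that the regimes differ in timing.

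Add that four visits can locate timing only between visits. If one timespan per outcome is still wanted, the size of change that counts must be set in advance.

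The cost is SAP wording and slightly more reporting; no new data, visits or model family are needed. The downside is wide intervals for the 3-month segments (about ±0.37 ml/kg/min per month within an arm under the assumptions above, and about √2 times that, ±0.52, between arms). The gain lies in comparable units, visible uncertainty and a direct arm contrast.
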